2.7 A Summary Of Toxicology Data

In accordance with Scientific Advice from the European Medicines Agency, no safety pharmacology studies such as telemetry investigation have been performed; however, a modified Irwin Test was included in the 4-week rat toxicity study by eye drop administration.

The toxicology programme to date has included short-term intravenous studies, short-term ocular studies and four-week ocular studies, again in these species in rat and rabbit.

No causes for concern emerged from these toxicology studies. The systemic (intravenous) no-observed-adverse-effect level (NOAEL) in the rats and rabbits was shown to be 2.4 mg/kg while the local NOAEL in the same species was determined to be 1.2 mg/mL (equivalent to 6 µg per eye, three times daily).

For additional information regarding the development of rhNGF, consult the current Investigator Brochure (IB) [Reference: [4](#)].

2.8 Risk - Benefit Evaluation

In the present study, potential risks of multiple rhNGF applications to healthy male and female volunteers of Japanese ethnicity are not expected to surpass the frequency of adverse reactions and untoward effects previously reported in the Phase I/II studies.

The results of this study will allow development of rhNGF for use in the treatment of eye conditions in subjects with Japanese ethnicity.

A Full Marketing Authorization for the treatment of stage 2 and 3 NK has been granted to rhNGF eye drops in July 2017 by the European Medicines Agency (EMA) in the European Union (EU), and the drug has been put on the European market in November 2017.

2.9 Description Of The Investigational Product

The investigational medicinal product (IMP) consists of a sterile isotonic solution for ocular administration (containing L-methionine as excipient), containing rhNGF 20 µg/mL as drug substance.

The matching placebo vehicle consists of a sterile isotonic solution containing L-methionine as excipient.

Further information is given in § 5.

3 OVERALL STUDY DESIGN AND INVESTIGATIONAL PLAN

3.1 Study Objectives

3.1.1 Primary Objective

The primary objective of this study is to assess the safety and tolerability of a single short-term and a multiple dose scheme of rhNGF when administered as eye drops in healthy subjects of Japanese ethnicity.

3.1.2 Secondary Objective

The secondary objective of this study is to assess the pharmacokinetics of single and multiple doses of rhNGF when administered as eye drops in healthy subjects of Japanese ethnicity.

The immunogenicity will be valuated by the determination of the anti-therapeutic antibodies.

3.2 Study Administrative Structure

This study will be performed at one study center located in in US, enrolling subjects of Japanese ethnicity. At the study center, the Principal Investigator (PI) will be responsible for ensuring that the investigation is conducted according to the signed Investigator agreement, the protocol, ICH-GCP guidelines [Reference: 1], and local regulations.

The PI at the study center will be responsible for the management of the study, which will consist of maintaining the study file and the subject records, corresponding with the IRB/IEC, and completing the case report forms (CRFs) and reporting SAEs within 24 hours of initial awareness.

3.3 Overall Study Design

This is a Phase I, randomized, double-masked, placebo-controlled eye drops administration study of rhNGF in healthy male and female subjects of Japanese ethnicity.

A total of 30 subjects will be randomized in a masked manner: 20 subjects on rhNGF group and 10 on placebo. A study eye will be assigned to each subject by random. In the study eye, the subjects will be treated with:

- rhNGF (active) in the rhNGF group.
- vehicle (placebo) in the vehicle group.

In parallel, the fellow-eye (non-study eye) will receive vehicle (placebo) treatment.

3.3.1 Rationale for Selection of dose, control group and treatment schedule in the study

The dose that is proposed for this study (20 µg /mL) has been already tested both in healthy volunteers for five consecutive days and subjects for up to six months.

This dose (20 µg /mL, 1 drop in each eye, six times daily) has also been used for 56 consecutive days in patients with Stage 2 and 3 Neurotrophic Keratitis (NGF0214), dry eye (study NGF0216) and in patients after cataract and refractive surgery (NGF0116). The same dose and duration has been used in the First In Human study with rhNGF in healthy volunteers (NGF0112).

Higher doses of rhNGF (up to 180 µg /mL) were administrated for 168 days to retinitis pigmentosa subjects (Study NGF0113).

4 SELECTION OF STUDY POPULATION

The Inclusion/Exclusion are intended to identify healthy male and female volunteers of Japanese ethnicity. At least 6 males as well as 6 females will be included in the study to ensure, that a sufficient number of each gender are present in each treatment group.

4.1 Inclusion Criteria

To be eligible for inclusion into this study, each subject must fulfil the following inclusion criteria.

Each subject must meet all of the following inclusion criteria at the pre-study Screening visit (within 20 days prior to admission in the Unit for the dosing period) in order to participate in this study.

1. Male or female subjects of Japanese ethnicity, aged between 18 and 60 years inclusive, who must have all four Japanese grandparents who were born in Japan.
2. Subject has to be able to communicate well with the investigator, understands and complies with the requirements of the study, and understands and signs the written volunteer informed consent form.
3. Subject's systemic and ocular medical history must be considered normal in the opinion of the investigator at the Screening and Baseline visits.
4. Best corrected distance visual acuity (BCDVA) score ≤ 0.00 LogMAR (≥ 83 ETDRS letters, 20/20 Snellen or 1.0 decimal fraction) in each eye at the Screening and Baseline visits.
5. Normal anterior segment on external and slit lamp examination in both eyes at the Screening and Baseline visits.
6. Normal posterior segment on fundus ophthalmoscopic examination in both eyes at the Screening and Baseline visits.
7. Subject must be considered in good systemic health in the opinion of the investigator at the Screening and Baseline visits, as determined by:
 - a. Subject's body mass index is between 18.5 and 30.4 kg/m² inclusive
 - b. A pre-study physical examination with no clinically significant abnormalities.
 - c. Vital signs within clinically acceptable ranges for the purposes of the study (sitting systolic blood pressure [BP] ≥ 90 mmHg and ≤ 150 mmHg; diastolic BP ≥ 50 mmHg and ≤ 95 mmHg; heart rate ≥ 40 and ≤ 100 beats per minute; oral body temperature $\geq 35.5^{\circ}\text{C}$ and $\leq 37.5^{\circ}\text{C}$).
 - d. An ECG with no clinically significant abnormalities.
 - e. Pre-study clinical laboratory findings within normal range or not deemed clinically significant in the opinion of the investigator if outside of the normal range
8. Woman subject who meets the criteria for post-menopausal stage (post menopause is defined as the period following peri-menopause, i.e. postmenopausal after 12 months without a menstrual period and with a serum FSH value within the reference range for postmenopausal females at Screening) or permanently sterilised (e.g. tubal occlusion, hysterectomy, bilateral salpingectomy) or woman subject using oral, injected or implanted hormonal methods of contraception or with a double barrier methods of contraception: condom and occlusive cap (diaphragm or cervical/vault caps) with spermicidal foam/gel/film/cream/suppository. A female condom and a male condom should not be used together as friction between the two can result in either product failing.
9. Male subjects with female partners of child-bearing potential must use 2 different forms of highly effective contraception throughout the study and for a further 3 months after the follow-up visit and all male subjects must be willing to avoid donating sperm during this time. The following methods of

contraception are considered to be highly effective: established use of oral, injected or implanted hormonal contraception; placement of an intrauterine device or intrauterine system; use of a barrier method of contraception (condom or occlusive cap with use of a spermicide); male sterilisation (post-vasectomy documentation of the absence of sperm in the ejaculate must be provided).

4.2 Exclusion Criteria

Subjects meeting any of the following criteria at Screening will be excluded from entry into the study:

1. Subject has had a clinically significant illness in the 6 weeks before screening in the opinion of the investigator.
2. Subject is not suitable to participate in the study in the opinion of the investigator
3. Subject has participated in any clinical study with an investigational drug/device within 3 months prior to the first day of dosing.
4. Subject has had a serious adverse reaction or significant hypersensitivity to any drug or chemically related compounds or has a clinically significant allergy to drugs, foods or other materials (in the opinion of the investigator).
5. Administration of any topical ocular (prescription or over the counter including artificial tears) or systemic medication including herbal product or fish oil preparations within 14 days before the first dose of study drug. Vitamins and mineral supplements not containing other substances are allowed until 96 hours before each dose if considered by the Investigator unlikely to interfere with the study results. Paracetamol at doses of at most 2 grams per day and ibuprofen at doses of at most 1200 mg per day for no more than 3 consecutive days or 6 non-consecutive days are allowed. Oral, injectable and implantable hormonal contraceptives are allowed without restrictions for female subjects. Longer exclusion periods apply for:
 - a. amiodarone and hydroxychloroquine (210 days),
 - b. monoclonal antibodies/ immunoglobulins/ other therapeutic proteins (120 days)
 - c. Experimental drugs with a half life known to the Study Unit: Five half lives plus 2 weeks
 - d. Experimental drugs with a half life unknown to the Study Unit: 120 days
 - e. chloroquine and flunarizine (100 days)
 - f. fluoxetine (75 days),
 - g. benzodiazepines different from midazolam, lorazepam and triazolam, chlorpromazine, mephenytoin, nortriptyline, phenobarbital, primidone, carbamazepine, phenytoin and phenprocoumon (35 days).
6. Subject has a significant history of drug/solvent abuse or a positive drugs of abuse test at any time during the study.
7. Subject has a history of alcohol abuse or currently drinks in excess of 28 units per week or has a positive alcohol breath test at any time during the study.
8. Subject is a smoker or has smoked in the 6 months prior to dosing.
9. Subject who has a positive human immunodeficiency virus (HIV) screen, hepatitis B screen or hepatitis C screen.
10. Subject has donated blood or blood products (e.g., plasma or platelets) within the 3 months prior to screening.
11. Subject has a partner who will be pregnant or breastfeeding during the study

12. Pregnant or breastfeeding female or those with a positive pregnancy test or who will not use a medically acceptable contraceptive method from selection and during the study
13. Subject having used corticosteroid sporadically in the last 30 days whichever the route of administration, or any medication by ocular or nasal administration route
14. Subjects diagnosed with any ocular disease other than refractive error
15. Subject with history of ocular surgery, including laser refractive surgery
16. Subject using a contact lens within 7 days prior administration of the first dose
17. Intraocular pressure (IOP) ≥ 22 mmHg in either eye at screening or baseline
18. Presence of any corneal opacity or corneal fluorescein staining >0.5 grade using the modified Oxford scale in either eye at screening or baseline
19. Schirmer's test without anesthesia ≤ 9 mm/5 minutes in either eye at screening or baseline
20. Tear film break up time (TFBUT) < 8 seconds in either eye at screening or baseline

Note: Alcoholic beverages should not be taken from 48 h before first drug administration until discharge from the Study center. There are also restrictions with regard to chewing gum, heavy exercise and smoking (See § 7.6).

5 STUDY MEDICATION

5.1 Presentation, Storage, Packaging Of The Investigational Medicinal Product

TEST PRODUCT	
IMP	Recombinant human nerve growth factor (rhNGF), containing L-methionine as excipient - 20 µg/mL vials
Manufacturer active substance	Dompé Farmaceutici S.p.A., Italy
Manufacturer finished product	Bulk drug product is manufactured by Patheon Italia S.p.A-Italy. Packaging and labelling is performed by PCI Inc. USA
Pharmaceutical form	Sterile buffered aqueous solution
Dose	Study Eye (For subjects randomized to rhNGF group) Day 1: One drop instilled into study eye (35 µL, corresponding to 0.70 µg of rhNGF). Day 2, 3, 4, 5, 6: One drop six times a day (every 2h) into study eye (210 µL, corresponding to 4.20 µg of rhNGF). Total dose in the study eye will be 31 drops (1085 µL, equivalent to 21.7 µg rhNGF) over 6 days .
Administration route	Ophthalmic

5.2 Presentation, Storage, Packaging Of The Vehicle Product

REFERENCE PRODUCT	
IMP	Placebo vehicle, containing L-methionine as excipient - Vehicle vials
Manufacturer active substance	Dompé Farmaceutici S.p.A., Italy
Manufacturer finished product	Bulk drug product is manufactured by Patheon Italia S.p.A-Italy. Packaging and labelling is performed by PCI Inc. USA
Pharmaceutical form	Sterile buffered aqueous solution
Dose	Study Eye (For subjects randomized to vehicle group) Day 1: One drop instilled into study eye (35 µL, corresponding to 0 µg of rhNGF]. Day 2, 3, 4, 5, 6: One drop six times a day (every 2h) into study eye (210 µL, corresponding to 0 µg of rhNGF). Total dose of placebo vehicle in the study eye will be 31 drops (1085 µL, 0 µg rhNGF) over 6 days. Fellow (non-study) Eye for all subjects Day 1: One drop instilled into fellow eye (35 µL, corresponding to 0 µg of rhNGF). Day 2, 3, 4, 5, 6: One drop six times a day (every 2h) into fellow eye (210 µL, corresponding to 0 µg of rhNGF). Total dose of placebo vehicle in the fellow eye will be 31 drops (1085 µL, 0 µg rhNGF) over 6 days.
Administration route	Ophthalmic

5.3 Formulation And Packaging

The Investigator will be provided with a Subject box containing vials of frozen IMP solutions ($-20 \pm 5^{\circ}\text{C}$) containing:

- rhNGF, at concentrations of $20 \mu\text{g}/\text{mL}$, for dosing the right or left eye (study eye), according to the randomization list, or
- vehicle (placebo) for dosing the right or left eye (study eye) and for dosing the non-study eye according to the randomization list.

For subjects randomized to the rhNGF treatment group, each Subject box will contain a a box of 6 vials of rhNGF (for one eye) and a box containing 6 vials of Vehicle for the fellow (non-study) eye.

For subjects randomized to the Vehicle treatment group, each Subject box will contain a box of 6 vials of Vehicle (for one eye) and a box of 6 vials of Vehicle for the fellow (non-study) eye.

A total of 60 kits (containing the treatment for right and left eye) will be supplied to the Pharmacy of the Clinical Unit.

Syringes and adaptors will be provided separately in single sterile polyethylene packages and may be kept at room temperature.

The syringe is used with an adaptor consisting of a connecting device with dual connections: one end for the syringe and one end for the vial.

The Investigator will need to:

1. Put the adaptor on the top of the vial (after removing the plastic seal) by piercing the septum
2. Put the syringe on adaptor inlet
3. Draw the solution contained in the vial with the syringe until this reaches its predetermined capacity
4. Remove the syringe and use it as a dropper to administer one drop of IMP into each eye

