5.4.2 Dose regimen

In all subjects both eyes will be treated; with one eye as the study eye.

- All subjects will receive either rhNGF or vehicle in the study eye (right or left) according to the randomization list.
- The fellow (non-study) eye will receive vehicle.

Both the subjects and the investigator/ophthalmologist will be masked to the study treatment and study eye randomization (see § 6.3)

The exact times of study drug administration, and comments, will be recorded on the appropriate page of the eCRF.

rhNGF 20 µg /mL:

For subjects randomized to rhNGF group:

Study Eye

- **Day 1:** One drop instilled into study eye (35 µL, corresponding to 0.70 µg of rhNGF).
- **Day 2, 3, 4, 5, 6:** One drop six times a day (every 2h) into study eye (210 µL, corresponding to 4.20 µg of rhNGF).

Total dose in the study eye will be 31 drops (1085 µL, equivalent to 21.7 µg rhNGF) over 6 days .

Vehicle:

For subjects randomized to vehicle group:

Study Eye

- **Day 1:** One drop instilled into study eye (35 µL, corresponding to 0 µg of rhNGF).
- **Day 2, 3, 4, 5, 6:** One drop six times a day (every 2h) into study eye (210 µL, corresponding to 0 µg of rhNGF).

Total dose of placebo vehicle in the study eye will be 31 drops (1085 µL, 0 µg rhNGF) over 6 days.

Fellow (non-study) Eye

For all subjects (subjects randomized to rhNGF group and subjects randomized to vehicle group):

- Day 1: One drop instilled into fellow eye (35 μ L, corresponding to 0 μ g of rhNGF).
- Day 2, 3, 4, 5, 6: One drop six times a day (every 2h) into fellow eye (210 μ L, corresponding to 0 μ g of rhNGF).

Total dose of placebo vehicle in the fellow eye will be 31 drops (1085 μ L, 0 μ g rhNGF) over 6 days.

5.5 Criteria For Schedule Adjustment/Dose-Modification/ Discontinuation Of Investigational Product

No schedule adjustment or dose adjustments are allowed.

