7.2 Study Visits And Follow-Up Assessments

Baseline (Day -1)

- Review of inclusion/exclusion criteria
- Current Medical conditions
- Physical examination
- Adverse Events
- Concomitant medication
- Vital signs (body weight, blood pressure, pulse rate, respiratory rate and ear body temperature) measured after at least 3 minutes in the sitting position.

- ECG (12 lead)
- Laboratory safety tests including: hematology, clinical chemistry and urine analysis
- Screening for drugs of abuse including alcohol breath test
- Pregnancy test for female subjects
- Blood samples for PK
- Blood sample for ATA
- Ocular examination (both eyes):
 - BCDVA Assessment of LOT (VAS: foreign body sensation, burning/stinging, itching, pain, sticky feeling, blurred vision, photophobia)
 - EOE: motility and eyelids
 - SLE to assess the eyelid margin, conjunctiva, cornea, anterior chamber, iris and lens (Note: The SLE must be performed before IOP)
 - CFS (modified Oxford scale) following instillation of fluorescein
 - TFBUT
 - Schirmer test (ST) without anesthesia
 - Intraocular pressure (IOP)
 - Dilated Fundus Ophthalmoscopic (FO) examination to assess the vitreous, retina/macula/choroid, and optic nerve, including cup/disc ratio

Treatment Day 1

One drop of rhNGF or vehicle instilled into one eye on day 1 (35 µL).

- Adverse Events
- Concomitant Medication
- Vital signs (body weight, blood pressure, pulse rate, respiratory rate and ear body temperature) measured after at least 3 minutes in the sitting position.
- ECG (12 lead)
- Ocular examinations (both eyes):
 - BCVDA
 - EOE: motility and eyelids
 - Assessment of LOT (VAS: foreign body sensation, burning/stinging, itching, pain, sticky feeling, blurred vision, photophobia)
 - SLE to assess the eyelid margin, conjunctiva, cornea, anterior chamber, iris and lens
 - CFS (modified Oxford scale) following instillation of fluorescein
 - TFBUT
- Blood samples for PK
- Randomization
- Study drug administration

Treatment Day 2

One drop of rhNGF or vehicle instilled into one eye six times a day on 2,3,4,5,6 (every 2h; 210 µL, corresponding to 4.20 µg of rhNGF).

- Adverse Events
- Concomitant Medication
- Vital signs (body weight, blood pressure, pulse rate, respiratory rate and ear body temperature) measured after at least 3 minutes in the sitting position.
- ECG (12 lead)
- Ocular examinations (both eyes):
 - BCVDA
 - EOE: motility and eyelids

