7.2.7 Primary and Secondary Tolerability Endpoints

*A global ocular discomfort score will be assessed by the subject using a self-administered 100 mm visual analogue scale (VAS) on which 0 means no symptoms and 100 means the worst possible discomfort. This evaluation is to be performed **before** any ophthalmic assessment at a given study visit.*

The VAS Ocular tolerability scores will be collected on the eCRF page “Visual Analogue Scale Ocular Tolerability” per eye for the symptoms:

- Foreign body sensation
- Burning/stinging
- Itching
- Ocular pain
- Sticky feeling
- Blurred vision
- Photophobia

The assessments should be performed at Baseline Visit 0hr, D1 8hr, D2 Pre-Dose, D2 8hr, D3 Pre-Dose, D6 Pre-Dose, D6 8hr, FU1 0hr, FU2 8hr, Fu3 0hr.

The Overall VAS Ocular Tolerability Score acts as a global discomfort score and is defined as the mean of all VAS Ocular Tolerability symptom scores per visit per eye. In case of missing symptom scores, the mean will be calculated on the remaining VAS scores if at least 5 out of 7 scores are non-missing.

The primary tolerability endpoints for the assessment of the single dose scheme are defined as Change from Baseline of the D2 Pre-Dose value in the study eye. Baseline is defined as the corresponding assessment at Baseline Visit 0hr. This will be derived for the Overall VAS Ocular Tolerability Score as well as for each single symptom scale.

The primary tolerability endpoints for the assessment of the multiple dose scheme are defined as Change from Multiple Dose Baseline, i.e. the difference between the considered VAS score in the study eye at D2 8hr, D3 Pre-Dose, D6 Pre-Dose, D6 8hr, FU1 0hr, FU2 8hr, Fu3 0hr and the D2 Pre-Dose value in the study eye. This will be derived for the Overall VAS Ocular Tolerability Score as well as for each single symptom scale.

Secondary tolerability endpoints are:

- the raw VAS ocular tolerability scores in Study Eye and Non-Study Eye at all scheduled visits.
- the intra-individual differences in VAS ocular tolerability scores between Study Eye and Non-Study Eye at all study visits.

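### Protocol 5.3 step 4, read literally, puts drops from one vial into both eyes, which contradicts the paired-eye regimen elsewhere; the passages need to be reconciled

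*Protocol*

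**What the plan says.** Protocol 5.3 lists four administration steps. The adaptor goes on the vial and the syringe on the adaptor; then "Draw the solution contained in the vial with the syringe until this reaches its predetermined capacity"; then "Remove the syringe and use it as a dropper to administer one drop of IMP into each eye". Vial and syringe are singular throughout. No step says to repeat the sequence with a second vial or to match the vial to the eye.

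Earlier in the same section, the supply for an rhNGF subject is "a box of 6 vials of rhNGF (for one eye) and a box containing 6 vials of Vehicle for the fellow (non-study) eye". Section 5.3.1 gives every vial label a line naming the right or left eye.

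On the regimen, 5.4.2 states "The fellow (non-study) eye will receive vehicle", with 0 µg of rhNGF over 31 drops. Sections 5.2 and 6.2 agree.

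The Day 1 line in 7.2 reads "One drop of rhNGF or vehicle instilled into one eye on day 1". The Day 2 to 6 lines have the same form, and none mentions the fellow eye. The schedule in 1.1 and Appendix 3 both state the fellow-eye vehicle drop.

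Section 5.3.2 refers preparation and administration to a separate Pharmacy Manual.

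**The concern.** The paired-eye layout is what makes the fellow eye a within-subject control. One secondary tolerability endpoint rests on it directly: "the intra-individual differences in VAS ocular tolerability scores between Study Eye and Non-Study Eye at all study visits". Ocular TEAEs are also reported by eye. PK and systemic safety are read against a stated rhNGF dose in one eye.

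A printed step that would deliver the wrong product if followed as written is more than missing detail. The each-eye/one-eye wording also wavers elsewhere. Protocol 3.3.1 describes earlier use of this dose in neurotrophic keratitis, dry eye and surgery patients as a drop in each eye, while the matching six-times-daily rows of Table 2 in 2.6 say one eye.

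The planned exposure analysis would not reveal a wrong-vial drop. SAP 7.2.4 counts administration records by eye and does not count by product.

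**Working it through.** **Inputs.** Concentration 20 µg/mL and drop volume 35 µL; one drop on Day 1 and six a day on Days 2 to 6 (Protocol 5.4.2). Vial volume 1 mL (5.3.1). Overdose defined as more than 3 times the total daily dose (9.8). Compliance is 100 × drops / 30 per eye for the multiple-dose scheme (SAP 7.2.4).

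**The protocol's own figures.**
- Per drop: 35 µL × 20 µg/mL = 0.70 µg.
- Daily, Days 2 to 6: 6 × 0.70 = 4.20 µg in 6 × 35 = 210 µL.
- Drops: 1 + 5 × 6 = 31. Volume: 31 × 35 = 1085 µL. Total: 31 × 0.70 = 21.7 µg.

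All match 5.4.2.

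**Step 4 taken literally, rhNGF vial used for both eyes.** If this happens on k of the 31 occasions and the others go as planned, the subject's total is 21.7 + 0.70 × k µg.

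| k | Fellow eye, rhNGF | Subject total | Ratio to stated |
|---|---|---|---|
| 0 | 0 µg | 21.7 µg | 1.0 |
| 6 (one multiple-dose day) | 4.2 µg | 25.9 µg | 1.2 |
| 31 | 21.7 µg | 43.4 µg | 2.0 |

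At k = 31 the daily amounts are 2 × 0.70 = 1.40 µg on Day 1 and 12 × 0.70 = 8.40 µg on Days 2 to 6. The study eye stays at 21.7 µg throughout.

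**Opposite case.** The steps do not say which vial is opened. If it were the vehicle vial each time, the subject would receive 0 µg. The factor of 2.0 is therefore one end of a range.

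**Would something in the plan stop or show it?**
- Vial volume would not: 12 × 35 = 420 µL is less than 1000 µL.
- The overdose rule would not: 8.40 µg is below 3 × 4.20 = 12.6 µg, and on Day 1 1.40 µg is below 3 × 0.70 = 2.1 µg.
- SAP compliance would not: 30 recorded drops in the fellow eye give 100 × 30 / 30 = 100%, whatever the vial held.
- If instead the 7.2 line were followed alone and the fellow eye got no drop, SAP compliance would show it: 100 × 0 / 30 = 0%.
- Supply records could: if one vial served both eyes, the other eye's box would remain unused (5.6 requires dispensing records and return of unused product).

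**Which results are exposed in the k = 31 case.** In up to 20 of the 30 subjects both eyes would be active, so the between-eye VAS difference would no longer contrast rhNGF with vehicle. Fellow-eye TEAEs and assessments would be those of an active eye, and PK and systemic safety would describe twice the stated amount. The primary tolerability endpoints are study-eye changes summarised by treatment group (SAP 10.6.2). The study-eye dose is unchanged and vehicle-arm subjects still have vehicle in both eyes, so that comparison keeps its control.

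**The case against.** The strongest reply is that this is loose drafting around an unambiguous design. The protocol's IMP label also covers vehicle (the IMP row in 5.2 is the placebo), so a drop of IMP into each eye can mean each eye's own assigned product. The boxes are separated by eye just above the steps, and every vial carries its eye. The 7.2 lines can be read as describing only the randomised study-eye treatment, since 210 µL and 4.20 µg are study-eye figures; section 7 also sends the reader to 1.1 and Appendix 3. Dosing is supervised (7.6.2), supplies are accounted for (5.6), and the blind data review checks treatment and study-eye assignment (SAP 8.3.3). The Pharmacy Manual, and the Protocol Clarifications of 21 May 2018 cited in SAP section 3, were not available here and may settle the matter.

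Most of this stands, and it lowers the likelihood of an error. It does not remove the contradiction. Section 5.3.2 does not say that the Manual overrides the printed steps, and SAP 3.6 lists no related change.

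A reader might go further and infer that rhNGF subjects would be dosed in both eyes, that nobody could notice, and that every by-eye table is compromised. The documents do not support this. Masking hides the contents of a vial, not the eye on its label, and study-eye tables still compare rhNGF with vehicle subjects.

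**Conclusion.** The contradiction is real and of moderate severity. It lies in the administration wording (5.3 step 4, and the omission in 7.2), not in the design. The figure of 43.4 µg against 21.7 µg is correct arithmetic, but it assumes that the rhNGF vial is used for both eyes on all 31 occasions. It is a worst case, not an expected dose. Under that assumption the within-subject comparison, fellow-eye results and the PK and systemic safety interpretation are affected in up to 20 of 30 subjects. The study-eye between-arm tolerability comparison and the vehicle arm are not. How the site was actually instructed cannot be judged without the Pharmacy Manual.

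**What to change.** The sponsor should reconcile 5.3 step 4 and the treatment-day lines in 7.2 with 5.4.2, Appendix 3 and the Pharmacy Manual, so that one consistent per-eye administration instruction applies. This review proposes no dose or dosing procedure.

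Optionally, the administration record could identify the labelled vial used for each eye at each instillation, so that the SAP 7.2.4 exposure tables can be given by product as well as by eye. If dosing has already taken place, the blind data review could check vial returns and dispensing logs by eye.

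The cost is a protocol clarification and a check of the Manual, plus one data field if the option is taken. Eye-specific boxes and labels already exist, so no new supplies are needed.
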